3.0 PATIENT ELIGIBILITY

3.1 Inclusion Criteria

- 3.1.1** Patients undergoing allogeneic bone marrow transplant for acute myeloid leukemia (AML), acute lymphoblastic leukemia (ALL), or myelodysplastic syndrome
- 3.1.2** Allogeneic transplant patients receiving either a fully myeloablative or reduced intensity chemotherapy +/- total body irradiation (TBI) conditioning regimen are eligible.
- 3.1.3** Allogeneic transplant patients receiving stem cells from a matched related, matched unrelated, mismatched unrelated, mismatched related (including haplotype matched) donors are eligible
- 3.1.4** Allogeneic transplant patients must be in a complete morphologic remission prior to transplant
- 3.1.5** Patients undergoing autologous bone marrow transplant for multiple myeloma
- 3.1.6** Myeloma patients must have achieved at least a very good partial remission prior to transplant and exhibit fewer than 10% plasma cells in their pre-transplant marrow biopsy
- 3.1.7** ≥ 18 years of age
- 3.1.8** Able to provide informed consent
- 3.1.9** Negative urine pregnancy test in women of child-bearing potential

3.2 Exclusion Criteria

Subjects meeting any of the exclusion criteria at baseline will be excluded from participating in this study.

- 3.2.1** Any woman who is pregnant or has reason to believe she is pregnant or any woman who is lactating.
- 3.2.2** Condition that makes MRI unsafe (e.g., cardiac pacemaker, epicardial pacemaker leads, cochlear implants, metal aneurysm clip, metal halo devices)
- 3.2.3** Inability to tolerate MRI (e.g., unable to lie flat for > 1 hour, severe claustrophobia)
- 3.2.4** Known allergy to fluorothymidine

3.2.5 Creatinine clearance < 40 ml/min, as estimated by the Cockcroft-Gault formula:

$$eC_{Cr} = \frac{(140 - \text{Age}) \times \text{Mass (in kilograms)} \times [0.85 \text{ if Female}]}{72 \times \text{Serum Creatinine (in mg/dL)}}$$

3.2.6 Poorly controlled diabetes mellitus (fasting blood glucose > 500 mg/dl)

3.2.7 Institutionalized subject (prisoner or nursing home patient)

3.2.8 Critically ill or medically unstable.

[figure not shown]
3.2.9 Currently hospitalized (All FLT-PET MRI scans will be obtained in the outpatient setting)

4.0 STUDY PLAN

4.1 Study Duration

It is anticipated that the total study duration encompassing recruitment, enrollment, and data analysis will take approximately 2 years. Active patient participation will last approximately 100 days. Patients will be followed for one year for the development of acute GVHD or graft failure.

4.2 Schema

This is a non-randomized prospective pilot study of patients who have undergone either allogeneic or autologous bone marrow transplants. Subjects will complete FLT-PET/MRI scans on transplant day +25 and on day +60 post-transplant. Only allogeneic transplant patients will undergo restaging marrow biopsies on days +35 and +100 as part of the usual standard of care.

4.3 Enrollment/Recruitment

We will plan to enroll a total of 15 patients in this study. Each patient will be asked to undergo two FLT-PET MRI scans as described above. The study patients who meet the eligibility criteria will be recruited by study personnel in the UNC Bone Marrow Transplant Program.

Once a patient has been referred, the patient will be approached by a coordinator to assess interest in participation. All eligible patients who agree to participate in the study will be asked to come to their scheduled appointment thirty minutes early to complete the informed consent process.

Review of the consent will take place in the privacy of an exam room, or when possible, a sample consent form will be sent to the patient via email prior to the patient's visit to allow for ample review. Once the patient has consented, women of child bearing potential (WCBP) will be given a urine pregnancy test in order to ensure that they are not pregnant.

We are currently seeking to perform a total of 30 FLT-PET MRI scans (two each on 15 patients). If, however, a patient(s) drops out of the study after completing only a single scan, additional patients may be approached for participation.

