4.4 FLT-PET/MRI

Experimental measurements will be obtained at two time points: On transplant day +25 +/- 5 days (immediately after neutrophil count recovery) and again on transplant day +60 +/- 5 days (a time point after stable count recovery). FLT PET/MR imaging will be performed. FLT will be obtained from the BRIC Radiochemistry Core. At each FLT-PET-MRI study visit, subjects will complete screening forms pertinent to both PET and MR.

A technologist will attempt to access an existing central venous catheter if appropriately credentialed personnel are on site. If necessary, however, a peripheral IV line will be placed. The patient will then be brought into the scanner room to initiate the scan. FLT (5 mCi) will be injected one hour prior to imaging and dynamic acquisitions will be obtained. Whole body PET/MR will be performed with conventional attenuation correction, whole body STIR (node identification). The MR portion of the scan will be simultaneously obtained *without* the use of gadolinium contrast agent.

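### The only stated pregnancy test is one urine test after consent; no repeat is stated before the second FLT injection, when that test is at least 25 days old

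*Combined protocol and SAP*

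**What the plan says.** Inclusion criterion 3.1.9 reads "Negative urine pregnancy test in women of child-bearing potential". Section 4.3 fixes when that test is done: "Once the patient has consented, women of child bearing potential (WCBP) will be given a urine pregnancy test", and gives its purpose: "in order to ensure that they are not pregnant". I read these as one and the same test.

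Exclusion criterion 3.2.1 covers "Any woman who is pregnant or has reason to believe she is pregnant or any woman who is lactating". The sentence that opens section 3.2 sets when it applies: "Subjects meeting any of the exclusion criteria at baseline will be excluded from participating in this study".

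Section 4.4 schedules two FLT injections, one for each scan, at day +25 ± 5 and day +60 ± 5. The only check it places at both visits is on paper: "At each FLT-PET-MRI study visit, subjects will complete screening forms pertinent to both PET and MR". It does not describe what the forms contain.

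Section 7.3.3 says what follows if a pregnancy is found or suspected on study: it is recorded as an SAE and the patient leaves the study at once. It schedules no test.

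**The concern.** The protocol treats fetal exposure to the tracer as something to prevent. It bars pregnant women, tests for pregnancy at entry, and discontinues any participant who becomes pregnant. The reason for the entry test applies equally to the second injection, but a single test informs only about the period around the day it is taken. Someone who conceives after consent without suspecting it could receive a second dose of an investigational radiotracer, with no stated test in the way.

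A lesser point is that the entry test is not tied to a window before the first injection either. Whether that matters depends on the day of consent, which is not stated.

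What is at stake is participant safety. The endpoints and the statistical analysis are untouched.

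**Working it through.** **Is a repeat test stated anywhere?** The places where one would be expected are these.

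| Section | What it schedules | Pregnancy test? |
|---|---|---|
| 3.1.9 and 4.3 | Urine test after consent | Yes, once |
| 3.2 | Exclusions, applied at baseline | No further test |
| 4.4 | PET and MR screening forms at each scan visit | None named |
| 5.1.1.2.1 (allogeneic) | Blood counts, metabolic panels, CMV and EBV loads | No |
| 5.1.1.2.2 (autologous) | Blood counts and metabolic panels after each scan | No |
| 6.1 table | Screening and consent (baseline only), scans, marrow biopsies | No row |
| 7.3.3 | Handling of a pregnancy on study | None scheduled |

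**How old is the entry test at each injection?** The inputs are the scan windows in 4.4.

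- Scan 1: 25 − 5 = day 20 to 25 + 5 = day 30.
- Scan 2: 60 − 5 = day 55 to 60 + 5 = day 65.
- Shortest interval between injections: 55 − 30 = 25 days.
- Nominal interval: 60 − 25 = 35 days.
- Longest interval: 65 − 20 = 45 days.

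Let k be the number of days from the consent test to scan 1. The test is k days old at injection 1 and between k + 25 and k + 45 days old at injection 2. As an eligibility test it cannot follow scan 1, so k ≥ 0. The protocol does not give k; the values below are assumed.

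| k (assumed) | Age at injection 1 | Age at injection 2 |
|---|---|---|
| 0 | 0 days | 25–45 days |
| 7 | 7 days | 32–52 days |
| 14 | 14 days | 39–59 days |

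**What do the documents suggest about k?** Section 4.2 describes "patients who have undergone either allogeneic or autologous bone marrow transplants", and 3.2.9 excludes current inpatients because "All FLT-PET MRI scans will be obtained in the outpatient setting". Together these make consent after discharge plausible, possibly on the day of scan 1. Section 3.1.1, however, speaks of patients undergoing transplant, which leaves earlier consent open. If consent came before day 0 (an assumption), the test would be more than 20 days old at injection 1 and more than 55 days old at injection 2. Only the 25-day minimum at injection 2 holds for every k.

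**The case against.** The strongest reply is that pregnancy status may well be checked at both visits. The PET and MR screening forms are completed each time and may ask about pregnancy. If a participant reports or suspects one, 7.3.3 takes her off study before the second injection. This stands as far as it goes: a known or suspected pregnancy is probably covered. It does not cover an unsuspected one, which self-report misses and a test is meant to find.

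A second reply is that the retest may be required somewhere this review cannot see: the consent form, the IND, or the imaging centre's procedures. That is possible, and nothing here shows that a retest is not done in practice. But 9.4 expects the study to be run as the approved protocol describes, so such a requirement should be traceable from the protocol, and no citation is given.

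A third is that conception within about two months of transplant conditioning is unlikely, that the sample may include few or no women of child-bearing potential, and that the tracer dose is small (at most 5 mCi and 6.1 µg, Appendix A). The documents give no probability with which to weigh the first two. The protocol nevertheless thought the entry test worthwhile in this same population at this same dose, and reduced-intensity conditioning is eligible (3.1.2). These arguments limit the likely size of the problem but do not explain why only one injection is covered.

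The point about the first injection is the weaker one. With the consent day unknown, it shows only that the timing is unspecified.

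**Conclusion.** The point holds. As written, the protocol permits a second FLT injection on a pregnancy test at least 25 days old, contrary to the purpose that 4.3 gives for testing. The 25-day bound assumes that both scans fall within their windows and that the entry test is done no later than scan 1.

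The finding is confined to what the available text states. It does not claim that pregnancy status goes unasked at the second visit, or that no outside procedure requires a retest. It puts no figure on the harm. It should be corrected because the remedy is cheap and serves the protocol's own aim.

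**What to change.** In 4.3 and 4.4, and as a new row of the 6.1 table, require a negative urine pregnancy test in women of child-bearing potential shortly before each FLT injection, with the window set by the clinical team. The consent test may serve for scan 1 if it falls inside that window. If a test is positive, withhold FLT and follow 7.3.3. If the IND or the imaging centre's procedures already require a pre-injection test, cite that requirement in 4.4 and 6.1 instead.

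The text change is one table row and one or two sentences. If all 15 participants were women of child-bearing potential, the extra tests would number 15 × 1 = 15 where the consent test serves for scan 1, or 15 × 2 = 30 where it does not. Each replacement patient adds one or two. The test can be done at the outpatient scan visit, and allogeneic patients already attend clinic two to three times a week through day 100. The drawback is that a scan will occasionally, though rarely, be missed.

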4.4 FLT-PET/MRI

Experimental measurements will be obtained at two time points: On transplant day +25 +/- 5 days (immediately after neutrophil count recovery) and again on transplant day +60 +/- 5 days (a time point after stable count recovery). FLT PET/MR imaging will be performed. FLT will be obtained from the BRIC Radiochemistry Core. At each FLT-PET-MRI study visit, subjects will complete screening forms pertinent to both PET and MR.

A technologist will attempt to access an existing central venous catheter if appropriately credentialed personnel are on site. If necessary, however, a peripheral IV line will be placed. The patient will then be brought into the scanner room to initiate the scan. FLT (5 mCi) will be injected one hour prior to imaging and dynamic acquisitions will be obtained. Whole body PET/MR will be performed with conventional attenuation correction, whole body STIR (node identification). The MR portion of the scan will be simultaneously obtained *without* the use of gadolinium contrast agent.

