5.1.1.3 FLT

FLT will be available through the Biomedical Research Imaging Center Radiopharmaceutical Laboratory as an investigational drug under and National Cancer Institute NCI IND. The associated risks and drug details are listed in Appendix A.

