9.4 Adherence to the Protocol

Except for an emergency situation in which proper care for the protection, safety, and well-being of the study patient requires alternative treatment, the study shall be conducted exactly as described in the approved protocol.

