1.4 Dosimetry

An ^{18}F FLT dose of 0.07 mCi/Kg with a maximum of 5 mCi was selected based on a prior human dosimetry study performed in 18 patients at the University of Washington⁵¹. With this dose, the individual organ and total-body radiation dose associated with ^{18}F FLT is comparable to or lower than those reported for widely used clinical nuclear medicine procedures. There is ample preliminary evidence that a dose of 5 mCi is sufficient for imaging. The actual dosing, 0.07 mCi/kg was determined by assuming average body weight of 70 Kg and dividing by the maximum total dose. As FLT is not lipid soluble, no upward adjustments are expected to be needed for subjects > 70 Kg. These details are specified in the IND. A summary of the relevant human dosimetry for 2 different voiding scenarios from the investigator's brochure is included in Table 1. For more details, the reader is referred to the IND.

Table 1. Human dosimetry estimates

Organ of Interest	Men mGy/MBq (mrad/mCi)	Women mGy/MBq (mrad/mCi)
Total Body Dose	Scenario 1 1.23E-02 (46)	Scenario 1 1.56E-02 (58)
	Scenario 2 1.26 E-02 (47)	Scenario 2 1.59 E-02 (59)
Bladder	Scenario 1 1.79E-01 (662)	Scenario 1 1.74E-01 (646)
	Scenario 2 7.91E-02 (293)	Scenario 2 7.76E-02 (287)
Liver	Scenario 1 4.51E-02 (167)	Scenario 1 6.42E-02 (238)
	Scenario 2 4.54 E-02 (168)	Scenario 2 6.45 E-02 (239)

Scenario 1: Single bladder voiding at 6 h after ^{18}F FLT administration with a 10% post-voiding bladder residual decayed to infinity. This scenario assumed no urine re-accumulation after 6 h.

Scenario 2: First bladder voiding at 2 h after ^{18}F FLT administration with a 10% post-voiding residual; urine re-accumulation between 2 and 6 h at a rate determined by the bladder curve fit; second bladder voiding at 6 h with a 10% post-voiding residual decayed to infinity. This scenario assumed no urine re-accumulation after 6 h.

The first scenario is conservative, whereas the second has a more realistic voiding scheme.

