1.6 Reported Adverse Events and Potential Risks

No adverse events have been reported for [¹⁸F]FLT at the dose to be used for this study. As described in section 6.2, non-radioactive FLT has been investigated as an anti-AIDS drug, and some adverse effects, namely, reversible peripheral neuropathy, were observed in subjects exposed to 50 ng-h/mL plasma over a course of 16 weeks (15 μ g/kg q12h). The FLT dose anticipated for this study will be <6.1 μ g for a single injection. Assuming a 70kg individual, the maximum concentration of FLT would be expected to be equivalent to 0.29 ng-h/mL. The radiation exposure associated with this study is described in section 3.3 and is comparable to the dose for other widely used clinical nuclear medicine procedures.

1.7 [¹⁸F]FLT Administered Dose

The administered dose will be 0.07 mCi/kg with a maximum of 5 mCi. The drug solution is stored at room temperature in a gray butyl septum sealed, sterile, pyrogen-free glass vial and has an expiration time of 8 hours. The injectable dose of [¹⁸F]FLT for most studies will be \leq 0.07 mCi/kg of fluorine-18, not to exceed 5 mCi with a specific activity greater than 200 Ci/mmol at the time of injection. In the dose of [¹⁸F]FLT, only a small fraction of the FLT molecules are radioactive. The amount of injected drug is \leq 6.1 μ g (\leq 25 nmol per dose) of FLT. [¹⁸F]FLT is administered to subjects by intravenous injection of \leq 10 mL. There is no evidence that nonradioactive and radioactive FLT molecules display different biochemical behavior.

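### Section 4.4 orders 5 mCi of FLT with no weight term, while Appendix A doses at 0.07 mCi/kg capped at 5 mCi; the two conflict below about 71 kg

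*Combined protocol and SAP*

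**What the plan says.** Section 4.4 (FLT-PET/MRI) describes what is done at each imaging visit: "FLT (5 mCi) will be injected one hour prior to imaging and dynamic acquisitions will be obtained". It has no per-kilogram term, does not call 5 mCi a maximum, and does not refer to Appendix A.

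Appendix A gives a weight-based rule in two places. Section 1.7, on the administered dose, says "The administered dose will be 0.07 mCi/kg with a maximum of 5 mCi", and then repeats the rule as an upper limit: "0.07 mCi/kg of fluorine-18, not to exceed 5 mCi with a specific activity greater than 200 Ci/mmol at the time of injection". Section 1.4 (Dosimetry) gives the reason: an "FLT dose of 0.07 mCi/Kg with a maximum of 5 mCi was selected based on a prior human dosimetry study". It derives the per-kilogram figure from the 5 mCi maximum and an average weight of 70 kg, and says of heavier patients that "no upward adjustments are expected to be needed for subjects > 70 Kg".

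Two other sections bear on which text governs. Section 5.1.1.3, in the risk chapter, says "The associated risks and drug details are listed in Appendix A". Section 9.4 requires, apart from emergencies, that "the study shall be conducted exactly as described in the approved protocol". The eligibility criteria (3.1 and 3.2) set no minimum or maximum weight, and section 4.3 plans two scans per patient.

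**The concern.** A dose and a dose ceiling are different instructions. Anyone working from section 4.4 injects 5 mCi into every patient; anyone working from Appendix A injects less into every patient light enough that the ceiling does not apply. Appendix A 1.4 dispenses with an increase above 70 kg, but nothing dispenses with the reduction below it. Section 9.4 does not settle the matter, because both texts belong to the approved protocol and a lighter patient cannot be dosed exactly as both describe.

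At stake are the clarity of a dose instruction for an investigational agent given under an IND, and some extra radiation for lighter patients at both scans. The statistical conclusions are not at stake.

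**Working it through.** **Inputs**

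- Section 4.4: 5 mCi at any weight.
- Appendix A 1.4 and 1.7: dose = min(0.07 × weight in kg, 5) mCi.
- Appendix A 1.4: 0.07 mCi/kg comes from a 5 mCi maximum and a 70 kg average weight.
- Appendix A Table 1, total-body dose, scenario 2 (the higher of the two scenarios for this organ): 59 mrad/mCi (1.59E-02 mGy/MBq) for women and 47 mrad/mCi for men.
- Section 4.3: two scans per patient.
- Weights of 50, 60 and 70 kg are illustrative; the documents give no weight distribution.

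**Step 1. Reproduce the plan's per-kilogram figure.** 5 / 70 = 0.0714, which rounds to the stated 0.07 mCi/kg.

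**Step 2. Find where the two instructions meet.** The ceiling applies when 0.07 × weight ≥ 5, that is from 5 / 0.07 = 71.4 kg. At or above this weight both texts give 5 mCi.

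**Step 3. Compare the doses below that weight.**

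| Weight | Appendix A dose | Section 4.4 dose | Excess | Ratio |
|---|---|---|---|---|
| 70 kg | 0.07 × 70 = 4.9 mCi | 5 mCi | 0.1 mCi | 5/4.9 = 1.02 |
| 60 kg | 0.07 × 60 = 4.2 mCi | 5 mCi | 0.8 mCi | 5/4.2 = 1.19 |
| 50 kg | 0.07 × 50 = 3.5 mCi | 5 mCi | 1.5 mCi | 5/3.5 = 1.43 |

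The 2% gap at 70 kg comes from rounding 0.0714 to 0.07. Rounding does not explain the gaps of 19% and 43%.

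**Step 4. Convert the excess to total-body dose per scan** (excess activity × coefficient).

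- Women: 60 kg, 0.8 × 59 = 47.2 mrad; 50 kg, 1.5 × 59 = 88.5 mrad.
- Men: 60 kg, 0.8 × 47 = 37.6 mrad; 50 kg, 1.5 × 47 = 70.5 mrad.
- Check for women in SI units, at 37 MBq per mCi: 0.8 × 37 × 0.0159 = 0.47 mGy; 1.5 × 37 × 0.0159 = 0.88 mGy. These agree with the figures above.

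**Step 5. Over both scans, women.** 2 × 47.2 = 94.4 mrad at 60 kg; 2 × 88.5 = 177.0 mrad at 50 kg.

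**Step 6. Check the mass limit.** At the minimum specific activity in Appendix A 1.7, 5 mCi / 200 Ci/mmol = 25 nmol, which equals the stated per-dose limit. Following section 4.4 would therefore not breach the mass limit.

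**The case against.** The best defence is that the plan does contain the full rule, in the section meant for it. Appendix A 1.7 is the dosing section, section 5.1.1.3 sends the reader to Appendix A for drug details, and a specific dosing section would ordinarily prevail over a figure in parentheses within a procedural narrative. The 5 mCi in section 4.4 may well be nominal shorthand: it never says the dose is fixed regardless of weight, and Appendix A 1.4 itself speaks of 5 mCi as sufficient for imaging. The appendix also says the dosing details are in the IND, so the order staff actually use may be clear in a document not available here.

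On harm, any excess arises only if staff follow section 4.4 for a patient under 71.4 kg. Even then the activity stays at the ceiling. Appendix A 1.5 reports earlier human studies using 1.4 to 13 mCi, and 1.6 reports no adverse events at the study dose.

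Much of this stands. It limits the consequence, and it rules out any claim that over-exposure has been shown. It also makes this an internal inconsistency rather than a disputed design choice. It does not remove the conflict. Section 4.4 does not say that 5 mCi is a maximum, the pointer in 5.1.1.3 sits in the risk chapter and sets no order of precedence, and an IND that the reader has to consult does not correct the protocol's own text.

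**Conclusion.** The concern holds, as a minor point. Sections 4.4 and Appendix A give different doses for any patient under 71.4 kg, and the protocol does not say which applies. Following section 4.4 would give 19% more activity than Appendix A specifies at 60 kg and 43% more at 50 kg, at each of two scans. At or above 71.4 kg there is no difference.

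The radiation figures describe what would happen if section 4.4 were followed literally. They assume that the Table 1 coefficients apply unchanged to lighter patients. How many of the 15 patients would be affected cannot be said without a weight distribution.

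The primary measures are standardized uptake values. The documents do not give the SUV formula, and no bias in the endpoints is claimed. Nothing in the sample-size section depends on the injected activity.

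**What to change.** In section 4.4, replace the activity in parentheses with the appendix rule and a reference: 0.07 mCi/kg, maximum 5 mCi, see Appendix A 1.7. If the sponsor does intend 5 mCi for everyone, Appendix A 1.4 and 1.7 should be changed to say so, and agreement with the IND confirmed. The first option is preferable because it restates a rule the protocol already contains and avoids the extra exposure in lighter patients.

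The cost is a one-line wording change, with no effect on the analysis, sample size or visit schedule.
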